### Post Treatment Follow-up:

Each subject will be followed up for at least 6 months after cessation of pegloticase infusions. If these 6 months occur prior to end of study at Week 52, such as in the case of a subject who ends pegloticase infusions on or before Week 24, there will be no follow-up visits after the Week 52/End of Study Visit. For subjects who end pegloticase infusions between Weeks 26 and 36, there will be at least 3 months of follow-up while the subject remains on-study prior to Week 52, and then one follow-up visit after the Week 52/End of Study Visit. For subjects who end pegloticase infusions between Weeks 38 and 52, there will be two follow-up visits at intervals of 3 months after the Week 52/End of Study Visit.

### 9.3.3.2 Removal of Subjects From Study

In addition to completion of therapy and designated study visits through Week 52, the reason for discontinuation from the study should be recorded on the eCRF using 1 of the following categories:

- Lost to Follow-up. The subject does not return to the clinic for scheduled assessments, and does not respond to the site's attempts to contact the subject.
- Withdrawal of Consent. The subject withdraws from the study. The clinical site should attempt to determine the underlying reason for the withdrawal and document it on the eCRF; (i.e. AE, voluntary withdraw), Specify.
- Study Terminated by Sponsor. The Sponsor, IRB, or regulatory agency terminates the study.

KRYSTEXXA IND: 010122

Death.

### 9.3.4 Replacement Policy

# **9.3.4.1 Subjects**

No subject prematurely discontinued from the study for any reason will be replaced.

### 9.3.4.2 Centers

A center may be closed and/or replaced for the following administrative reasons:

- Excessively slow recruitment.
- Poor protocol adherence.

#### 9.3.4.3 Screen Failures

Subjects who do not meet all of the inclusion criteria or meet any of the exclusion criteria will be considered screen failures. In addition, subjects who are unable to tolerate MTX at an oral dose of 15 mg weekly during the MTX Run-in Period will be considered screen failures. Screen failure subjects who are females of childbearing potential who took at least one dose of MTX, will receive a Safety Follow-up Phone call/E-mail/Site Visit approximately 30 days after the last dose of MTX to verify at least one ovulatory cycle after the last dose of MTX. If the subject has not ovulated, a urine pregnancy test will be performed at the study site. Screen failure subjects who receive at least 1 dose of MTX and are non-vasectomized males will receive a Phone/E-mail/Site Visit 3 months after MTX discontinuation regarding partner pregnancy.

Screen failure subjects may be allowed to rescreen for the study if both the Investigator and Sponsor are in agreement regarding rescreening and if the Investigator determines that the subject can satisfy all of the eligibility criteria.

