#### **Duration of Treatment and Follow-up:**

**Screening:** Completed within 2 weeks prior to the Week -4 visit

MTX Run-in Period (Week -4 through Day 1): Includes 4 weeks of MTX weekly dosing

**Pegloticase** + **IMM Period (Day 1 through Week 52)**: MTX dosed weekly and 50 weeks of pegloticase infusions visits every 2 weeks); Non-infusion visits at Weeks 1, 7 and 52.

KRYSTEXXA IND: 010122

**End of Pegloticase Infusions Visit (if applicable)**: If the subject discontinues pegloticase treatment prior to infusion Week 50, such as due to the sUA stopping rules, the subject will complete this visit within approximately 2 weeks of the last infusion. Subjects will continue study.

Week 52/End-of-study/Early Termination Visit: Week 52 or earlier if the subject withdraws consent to participate in the study.

Safety Follow-up Visits: All subjects will receive a safety follow-up phone call/e-mail/visit approximately 30 days after the last dose of pegloticase/MTX to assess if any SAE's have occurred. Subjects who receive at least one dose of MTX and are females of childbearing potential, will receive a safety follow-up phone call/e-mail/Site Visit approximately 30 days after the last dose of MTX to verify at least one ovulatory cycle has occurred after the last dose of MTX. If the subject has not ovulated, a urine pregnancy test will be performed. Subjects who receive at least one dose of MTX and are non-vasectomized males, a phone/e-mail/Site Visit inquiry will be conducted 3 months after MTX discontinuation regarding partner pregnancy (inquiry can occur during the 3 month Post Treatment Follow-up).

**3 and 6 Month Post Treatment Follow-up Visits:** All subjects will be followed for a minimum of 6 months following the last infusion, with follow-up after Week 52 as warranted.

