### 9.4.6.3.2.2 MTX Dose Titration Algorithm and Intolerance Criteria

During the MTX Run-in a subject will be considered a screen failure if any of the following new laboratory findings or symptoms reflecting MTX intolerance occur:

PRIVATE AND CONFIDENTIAL INFORMATION OF HORIZON THERAPEUTICS IRELAND DAC

Page 57 of 129

- 1. Abnormal Hematology findings:
  - a. WBC  $< 3.5 \times 10^9/L$
  - b. Platelets  $< 75 \times 10^9/L$
  - c. Hematocrit < 32%
- 2. Abnormal hepatic function findings:
  - a. AST/ALT >1.5 x upper limit of reference range and
  - b. Albumin < lower limit of reference range
- 3. Abnormal renal function: eGFR <40ml/min/1.73 m^2 (as estimated with the MDRD equation).
- 4. New clinically important signs and symptoms, such as the following:
  - a. Rash or oral ulceration
  - b. Persistent nausea, vomiting and diarrhea
  - c. New or increasing dyspnea or dry cough, or unexplained cough with fever
  - d. Severe sore throat, abnormal bruising
  - e. Severe headaches, fatigue, and problems concentrating

Note that if minor clinical symptoms emerge, such as mild stomatitis, mild GI discomfort, etc., the investigator may increase folic acid dose (e.g. 2 mg daily) or recommend a divided dose of MTX (e.g. 3 tabs of 2.5 mg in the morning and evening on the day of dosing); if symptoms improve, subject will not be considered a screen failure on the basis of that symptom.

During the Run-In and Pegloticase+IMM Period, MTX dose guidance based on new laboratory findings or new symptoms is as follows:

Lab Parameters	Value	MTX Dose Change
WBC	$3.0 \times 10^9/L \sim 3.5 \times 10^9/L$	Decrease to 10 mg
	< 3.0 x 10  /L	Temporary stop
Platelets	< 50 x 10  /L	Temporary stop
Hematocrit	< 27%	Temporary stop
AST/ALT	Between 1.5 ~ 2 x ULN	Decrease to 10 mg
	> 2 x ULN	Temporary stop
eGFR	< 30 ml/min/1.73 m 	Temporary stop
New clinically important symptoms/signs*	Yes	Temporary stop

\* New clinically important symptoms or important medical events:

KRYSTEXXA IND: 010122

- a. Rash or oral ulceration
- b. Persistent nausea, vomiting and diarrhea
- c. New or increasing dyspnea or dry cough, or unexplained cough with fever
- d. Severe sore throat, abnormal bruising
- e. Severe headaches, fatigue, and problems concentrating

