## 9.5.6.1.3 Week -2

- Confirm study eligibility through review of the inclusion/exclusion criteria (see Section 9.3).
- Obtain blood samples for hematology and clinical chemistry analysis.
- Obtain a urine sample for uric acid:creatinine ratio.
- Obtain a urine sample from all females of childbearing potential for performance of a pregnancy test.
- Obtain a blood sample for measurement of sUA (only 1 sample for central laboratory).
- Assess MTX compliance and re-dispense MTX.

KRYSTEXXA IND: 010122

- Document gout flares and intensity.
- Ask Yes/No question regarding folic acid and gout flare prophylaxis compliance.
- Fill gout prophylaxis, fexofenadine, acetaminophen, and folic acid prescriptions, as needed.
- Collect substance use history, and medication history (see Section 9.4.9 for restrictions regarding medications).
- Inquire about AEs.
- Screen failure subjects that taken MTX during Week -4 or Week -3, Week -2 or Week -1, and who are females of childbearing potential, will receive a safety follow-up phone call/e-mail/site visit approximately 30 days after the last dose of MTX to verify at least one ovulatory cycle has occurred since the last dose of MTX. If the subject has not ovulated, a urine pregnancy test will be performed. Screen failure subjects who are non-vasectomized males, a phone/e-mail/site visit inquiry will be conducted 3 months after MTX discontinuation regarding partner pregnancy.

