#### 9.6.7 Safety Analysis

Treatment-emergent AEs (TEAEs) during the Run-In period are defined as events with an onset date on or after the first dose of MTX through the first pegloticase infusion, or 30 days after the last dose of MTX for subjects who do not receive pegloticase. TEAEs during the Pegloticase + IMM Period are defined as events that occur after the start of the first pegloticase infusion through 30 days after the last dose of pegloticase and/or MTX (whichever is later). TEAEs during the MTX Run-in Period will be summarized with the ITT population, and TEAEs during the Pegloticase + IMM Period will be summarized with both the ITT and mITT populations. TEAEs during any period (MTX Run-in Period or Pegloticase + IMM Period) will be summarized for the mITT population. AEs that occur more than 30 days after the last dose of pegloticase and/or MTX through the 6 month follow-up visit will also be summarized. The number and percentage of subjects experiencing AEs will be summarized by system organ class and preferred term. Summaries by maximum severity and relationship to MTX and pegloticase

Protocol: HZNP-KRY-201

KRYSTEXXA IND: 010122

Version 3.0, Administrative Change 1

will also be provided. SAEs and AEs leading to discontinuation of MTX and pegloticase will be presented by system organ class and preferred term.

Incidence of IRs, gout flares, and other AEs of special interest will be summarized.

Laboratory test results, including urine uric acid:creatinine ratio, will be summarized by study visit and change from baseline. Shift tables for laboratory parameters by Common Terminology Criteria for Adverse Events grade will be presented. Laboratory test results will also be classified relative to the normal reference range (normal, low, or high).

Vital signs, including blood pressure, respiratory rate, temperature, and heart rate, will be summarized by study visit and change from baseline.

Prior and concomitant medications will be summarized and/or included in the data listings.

Data for the MTX Run-in Period and Pegloticase + IMM Period will be summarized separately, where applicable.

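### Run-in adverse events are counted to 30 days after the last MTX dose in never-infused subjects, but no scheduled contact collects non-serious events after a run-in failure's last visit

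*Protocol*

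**What the plan says.** **What is reported.** Section 9.6.2 defines ITT by at least one MTX dose, so run-in failures belong to it. Section 9.6.7 summarizes run-in TEAEs on ITT, without restricting them to serious events. For subjects never infused, the window closes at the first infusion "or 30 days after the last dose of MTX for subjects who do not receive pegloticase".

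**Who leaves in the run-in.** Section 9.4.6.3.2.2 states: "During the MTX Run-in a subject will be considered a screen failure if any of the following new laboratory findings" or symptoms of MTX intolerance appear. Section 9.3.4.3 agrees that "subjects who are unable to tolerate MTX at an oral dose of 15 mg weekly during the MTX Run-in Period will be considered screen failures".

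**What the screen-failure text schedules.** Section 9.3.4.3 states: "Screen failure subjects who are females of childbearing potential who took at least one dose of MTX, will receive a Safety Follow-up". This contact is made "approximately 30 days after the last dose of MTX to verify at least one ovulatory cycle after the last dose of MTX". Non-vasectomized men "will receive a Phone/E-mail/Site Visit 3 months after MTX discontinuation regarding partner pregnancy". The Week -4 and Week -2 visit instructions (9.5.6.1.2 and 9.5.6.1.3) name the same two contacts.

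**What is said elsewhere.** The synopsis, under Duration of Treatment and Follow-up, states: "All subjects will receive a safety follow-up phone call/e-mail/visit approximately 30 days after the last dose of pegloticase/MTX", to assess serious events. Section 9.5.6.5 and footnote 10 of the Schedule of Assessments place that serious-event review 30 days after the last MTX dose. The schedule's column for the visit is headed by the last pegloticase infusion instead. Section 9.5.4.1.2 runs adverse-event collection to the 6-month post-treatment visit.

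**The concern.** A TEAE table describes a period in which subjects were asked about events. For run-in failures, the analysis section fixes a period that the visit instructions do not cover. The site text closest to the situation offers only pregnancy questions, and offers none to vasectomized men or to women not of childbearing potential. The general 30-day contact is wider, but its text asks only about serious events.

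At stake is the run-in safety table. Run-in failures stay in its denominator for the full 30 days after the last dose, while a non-serious event starting after their last visit reaches the numerator only if it surfaces by chance. They are also the subjects selected for not tolerating MTX, so any shortfall makes MTX look better tolerated than it was. The statistical analysis plan cannot repair this, because it cannot supply events that nobody asked about.

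**Working it through.** The protocol gives no figure for this point, so the check sets the sections side by side and then does one small calculation.

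**1. Does any scheduled contact cover non-serious events after exit?**

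| Contact | Who | Timing | Stated content |
|---|---|---|---|
| 9.3.4.3, 9.5.6.1.2, 9.5.6.1.3 | Women of childbearing potential | About 30 days after last MTX | Ovulation; pregnancy test if needed |
| Same sections | Non-vasectomized men | 3 months after MTX stops | Partner pregnancy |
| Synopsis, Duration of Treatment and Follow-up | All subjects | About 30 days after last pegloticase/MTX | Serious events |
| 9.5.6.5 | Subjects | 30 days after last MTX | Serious events; ovulation where relevant |
| Schedule, footnote 10 | Not limited | 30 days after last MTX | Serious events |
| Schedule, column heading | Not limited | 30 days after last infusion | Undefined if never infused |
| 3- and 6-month post-treatment visits | Subjects, after final infusion (footnote 26) or Week 52 | Undefined if never infused | All adverse events |

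No row has text giving a never-infused subject an inquiry about non-serious events after the last run-in visit. The men's 3-month contact also comes about two months (roughly 90 − 30 = 60 days) after the TEAE window has closed.

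**2. When does collection end for a never-infused subject?** Section 9.5.4.1.2 ends it at the 6-month visit, which footnote 26 counts from the final infusion. Sections 9.3.3.1.1 and 9.5.6.7 place follow-up visits relative to the end of infusions and Week 52. With no infusion, the end date does not exist.

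**3. How much of the window follows the last inquiry?** Let d be the days from the last MTX dose to the last run-in visit attended. The part of the 30-day window left is 30 − d. Assume exit at a run-in visit within a week of the last weekly dose:
- d = 0: 30 days left, 30/30 = 100%
- d = 3: 27 days left, 27/30 = 90%
- d = 7: 23 days left, 23/30 = 77%

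A subject who took only the Week -4 dose and left at Week -2 has d = 14, leaving 16 days (16/30 = 53%). These are shares of calendar time under assumed exit dates. They say nothing about how many events begin then.

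**4. How much does one subject weigh?** Section 9.6.9 plans 12 to 16 subjects. If the ITT population is about that size, one subject is 1/16 = 6.3% to 1/12 = 8.3% of the denominator. The weight is smaller if run-in failures come on top of the planned number. A late event changes a preferred-term row only if that subject did not already have the same term.

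**The case against.** A reader might infer that run-in failures receive only pregnancy-related follow-up and that MTX harms in them go uncollected. The documents do not support that, for four reasons.

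- The synopsis gives the 30-day contact to all subjects, and section 9.5.6.5 repeats it for subjects with no limit by sex, fertility or infusion. Serious events are therefore covered if those words include screen failures. That reading is reasonable, since section 9.3.4.3 itself calls them subjects, but it is not certain: the schedule marks enrollment at Day 1, and 9.3.4.3 sets out a narrower follow-up without referring to the general one.
- The events that define intolerance are found at run-in visits. Adverse events are asked about and safety laboratory samples drawn at Week -4, Week -2 and Day 1, so the reason for exit is known at exit.
- Section 9.5.4.1.6 has the investigator proactively follow the subject once an event is recorded, reviews non-serious events still ongoing at the end of participation, and follows serious ones to resolution, stabilization or loss to follow-up. A claim that the abnormality behind the exit is left unfollowed would therefore be wrong, and no separate rule is needed for it.
- The adverse-event row of the schedule appears to be marked under the 30-day visit. That table is damaged in extraction, its column is counted from the last infusion, and footnote 10 names serious events for the visit, so this is weak support.

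These points stand and narrow the concern. They do not close it: the 30-day contact's text is limited to serious events, while section 9.6.7 counts all TEAEs, and section 9.5.4.1.6 concerns events already recorded rather than a new inquiry.

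**Conclusion.** The point holds in a limited form. The TEAE window for never-infused subjects and the scheduled collection do not agree, and late-onset, non-serious MTX events in run-in failures may be under-counted in the ITT run-in table. The direction is toward too few events.

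The size cannot be fixed from the document. It depends on the number of run-in failures, which is not stated, and on how often new non-serious events begin in the 23 to 30 days after the last inquiry (fewer if dosing stopped earlier). Those day counts should not be read as a fraction of events lost. In a study of 12 to 16 planned subjects even one affected subject is visible in a percentage table, but the primary endpoint and the on-infusion safety data are untouched.

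Two assumptions carry the conclusion: that the 30-day contact asks only what its text says, and that sites rely on scheduled inquiries for new non-serious events. This is worth correcting as a reconciliation of sections, not as a failure of safety oversight.

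**What to change.** Reconcile sections 9.3.4.3, 9.5.6.1.2, 9.5.6.1.3, 9.5.6.5 and 9.6.7, the synopsis text on follow-up, and the Schedule of Assessments (the 30-day column and footnote 10), so that they say the same three things:

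1. Every subject who took at least one MTX dose, screen failures included and regardless of sex or fertility, has the existing safety contact. For never-infused subjects it falls about 30 days after the last MTX dose.
2. That contact asks about adverse events and serious adverse events. The ovulation and partner-pregnancy questions remain as additions for the groups concerned.
3. For never-infused subjects, this contact ends adverse-event collection, in place of the 6-month visit that they do not have.

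Collection then matches the window already in section 9.6.7, which needs no change in length. The cost is one call or e-mail per run-in failure, wording changes in these places, and probably a few more recorded MTX events.

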#### 9.4 Treatments

#### 9.4.1 Treatments Administered

During the MTX Run-in Period, which begins 4 weeks prior to the first dose of pegloticase, subjects will take oral MTX at a dose of 15 mg weekly. Subjects will be instructed to take MTX weekly on the same day each week (if dosing more frequently than once in a day (i.e. BID, TID), the total MTX dose should be taken within 24 hours, preferably the same calendar day) and record the date and time of dose/s in the dosing calendar. During the Pegloticase + IMM Period, MTX should be taken 1 to 3 days prior to pegloticase infusion; however, if a subject does not do so, MTX must be taken ≥60 minutes prior to pegloticase infusion. During the MTX Run-in Period, if a dose is missed, it should be taken as soon as it is remembered. If it is within 48 hours of the next scheduled dose, the subject will be instructed to skip the missed dose and resume at the next regularly scheduled time; thus, subjects will be instructed not to double a dose to make up for a missed dose if within 48 hours of the next dose. During the Pegloticase + IMM Period, MTX should be taken 1 to 3 days prior to pegloticase infusion; however, if a subject does not do so, MTX must be taken ≥60 minutes prior to pegloticase infusion. If a subject becomes unable to

KRYSTEXXA IND: 010122

tolerate the prescribed dosage of MTX during the Pegloticase + IMM Period, the dosage may be decreased (see Section 9.4.6.3.2.2).

During the pegloticase +IMM Period all subjects will receive pegloticase at the same dose of 8 mg administered IV every 2 weeks for a total of 26 infusions from Day 1 through Week 50, inclusive (Pegloticase + IMM Period). The date and start and stop time of infusion including the flush will be recorded. Subjects will not be fasting on the day of infusion and will be encouraged to have a snack or normal meal before or after the infusion. All subjects will receive standardized prophylactic treatment to reduce the risk of acute gout flares, unless medically contraindicated or not tolerated, beginning ≥1 week before the first dose of pegloticase. Standardized IR prophylaxis consisting of pre-treatment with antihistamines, acetaminophen, and corticosteroids will accompany each infusion.

#### **9.4.1.1** Folic Acid

Subjects will take folic acid 1 mg orally every day beginning at Week -4 (the start of MTX) until prior to the Week 52/End of Study/Early Termination Visit.

If the subject discontinues pegloticase due to the stopping rules or other reason, MTX and folic acid should also be discontinued.

Prescriptions are to be filled at a local pharmacy, as needed. At study visits, the subject will be asked a Yes/No question whether folic acid was taken per protocol.

### 9.4.1.2 Gout Flare Prophylaxis

It is required that before a subject begins the Pegloticase + IMM Period, he or she has been taking at least one protocol standard gout flare prophylaxis regimen (i.e. colchicine and/or non-steroidal anti-inflammatory drugs and/or low-dose prednisone  $\leq 10$  mg/day) for  $\geq 1$  week before the first dose of pegloticase and continues flare prophylaxis per American College of Rheumatology guidelines [Khanna D et al. 2012] for the greater of 1) 6 months, 2) 3 months after achieving target serum urate (sUA < 6 mg/dL) for patients with no tophi detected on physical exam, or 3) 6 months after achieving target serum urate (sUA < 5 mg/dL) for patients with one or more tophi detected on initial physical exam that have since resolved.

Prescriptions are to be filled at a local pharmacy, as needed. At study visits, the subject will be asked a Yes/No question whether gout flare prophylaxis was taken per protocol.

### 9.4.1.3 Infusion Reaction Prophylaxis

Since IRs can occur with pegloticase, all subjects will receive IR prophylaxis prior to each infusion, consisting of an antihistamine, acetaminophen, and a corticosteroid. To standardize this regimen, subjects will receive fexofenadine (60 mg or 180 mg orally based on the Principal Investigator's discretion) the day before each infusion; fexofenadine (60 mg or 180 mg orally based on the Principal Investigator's discretion) and acetaminophen (1000 mg orally) the morning of each infusion; and methylprednisolone (125 mg IV) given over the infusion duration 10-30 minutes (recommended) or hydrocortisone (200 mg IV) will be administered immediately prior to each infusion. Substitution of the corticosteroid is not allowed. The name, dose, route,

Protocol: HZNP-KRY-201

KRYSTEXXA IND: 010122

Version 3.0, Adminstrative Change 1

date, and time of administration of each prophylactic medication will be recorded in the medical record and in the eCRF. Prescriptions are to be filled at a local pharmacy, as needed. The methylprednisolone or hydrocortisone used for IR prophylaxis will be supplied by the site. Other IR medications administered prior to each infusion may also be supplied by the site.

Prescriptions are to be filled at a local pharmacy, as needed. At study visits, the subject will be asked a Yes/No question whether IR prophylaxis was taken per protocol.

As a precaution, emergency equipment will be readily available to treat a possible hypersensitivity reaction, and will include drugs that would be used to treat an anaphylactic reaction. Personnel trained in managing IRs and, in the use of the emergency equipment will be readily available during, and for 1 hour after, the infusion. As IRs can occur after the completion of the infusion, subjects will be observed for 1 hour post-infusion.

